2.4.5 Analyses of safety data

The summary of safety results will be presented by treatment groups.

General common rules

All safety analyses will be performed on the safety population as defined in [Section 2.3.2](#), unless otherwise specified, using the following common rules:

- Safety data in patients who do not belong to the safety population (eg, exposed but not randomized) will be listed separately
- The baseline value is defined as the last available value prior to the first dose of study medication.
- The potentially clinically significant abnormality (PCSA) values are defined as abnormal values considered medically important by the Sponsor according to predefined criteria/thresholds based on literature review and defined by the Sponsor for clinical laboratory tests, vital signs, and ECG (PCSA in BTD-009536 version 3, see [Appendix C](#)).
- PCSA criteria will determine which patients had at least 1 PCSA during the TEAE period, taking into account all evaluations performed during the TEAE period, including nonscheduled or repeated evaluations. The number of all such patients will be the numerator for the on-treatment PCSA percentage
- The treatment-emergent PCSA denominator by group for a given parameter will be based on the number of patients assessed for that given parameter in the treatment-emergent adverse event period by treatment group on the safety population.
- For quantitative safety parameters based on central laboratory/reading measurements, descriptive statistics will be used to summarize results and change from baseline values by visit and treatment group. Summaries will include the endpoint value. The endpoint value is commonly defined as the value collected at the same day/time of the last dose of investigational product. If this value is missing, this endpoint value will be the closest one prior to the last dose intake.
- Analyses of the safety variables will be essentially descriptive, and no systematic testing is planned.

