
ASSESSMENT SCHEDULE
	
The study will consist of the following visits:
 
 
• Visit 1 (D-28-D-1): Screening
 
• Visit 2 (D1): Baseline, randomization, first study drug administration.
 
• Visit 3 to 11 (Week 2-Week 40): on treatment (during double-blind phase).
 
• Visit 12 (Week 52): End of Treatment (EOT) visit (last SC IMP administration at Week 50 and last oral IMP administration day before Visit 12).
 
• Visit 13 (Week 58): End of Study (EOS) visit.
 
 
At screening and baseline visits, a physical examination to assess disease activity and general health will be performed. Patients will be assessed for active or latent tuberculosis (TB) at baseline and during the study.
 
For an overview of the laboratory tests see the study flow chart below, which includes hematology, chemistry, lipids, glucose, insulin, antinuclear antibodies (ANA), glycosylated hemoglobin A1c (HbA1c), urinalysis, human immunodeficiency virus (HIV), Hepatitis B and C, serum and plasma for biomarkers and a 12-lead electrocardiogram (ECG). A serum pregnancy test for women of child bearing potential (WOCBP) will be obtained at screening as well. Future Use Sample (serum and plasma) used for future analysis (eg, circulating proteins) will be collected from each consenting patient using a separate informed consent form (optional). Blood samples (DNA and RNA for sequencing or gene expression [RNA only]) will be collected from each consenting patient using a separate informed consent form (optional).
 
Safety assessments are done at each study visit and include AEs, serious adverse events (SAEs) and adverse events of special interest (AESIs) including but not limited to neutropenia, thrombocytopenia, elevations in hepatic enzymes leading to

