- b Last administration of sarilumab is at Week 50. Patients will be monitored for at least 30 minutes or up to 2 hours as per country specific requirements after each dose of SC IMP for any signs or symptoms of a hypersensitivity reaction.
- c Patient Reported Outcomes include EQ-5D-3L, FACIT-Fatigue, SF-36v2, HAQ-DI
- d Bone Mineral Density assessment will be performed at the baseline (Visit 2) and Week 52 (Visit 12) using a DXA scan. The scan can be performed within ± 14 days of Visit 2 and within -14 days of Visit 12 and needs to include the lumbosacral and femoral neck regions. However, the baseline visit DXA scan is not required if there is one available within 12 weeks of baseline.
- e Chest X-ray is required during the screening period if no chest imaging (X-ray, CT, MRI) is available within the previous 12 weeks of V1 that clearly documents the exclusion of TB or if it does not follow the local guidelines and requirements for active screening of TB. In countries for which a specific approval procedure for the x-ray is required by a different committee than the local EC/IRB, a chest MRI between V1 and V2 can be performed.
- f Hematology (blood should be drawn before drug administration): Hemoglobin, hematocrit, red blood cell (RBC) count and morphology (if RBC count is abnormal), white blood cell (WBC) differential, platelet count, absolute neutrophil count (ANC).
- g Chemistry (blood should be drawn before drug administration): Sodium, potassium, chloride, bicarbonate, blood urea nitrogen (BUN), creatinine and creatinine clearance, calcium, phosphate, total protein, albumin, alanine aminotransferase (ALT) (SGPT), aspartate aminotransferase (AST) (SGOT), alkaline phosphatase (ALP), total bilirubin, conjugated bilirubin, unconjugated bilirubin, lactate dehydrogenase (LDH), uric acid
- h Anti-nuclear antibody (ANA) will be collected at Visit 2 and EOT visits only.
- i Lipids (blood should be drawn before drug administration): Triglycerides (TG), total cholesterol, high density lipoprotein (HDL) cholesterol, low density lipoprotein (LDL) cholesterol. Fasting is defined as having no food or liquid intake (except water/ice) for six hours or more.
- j Blood should be drawn before drug administration. Fasting is defined as having no food or liquid intake (except water/ice) for six hours or more.

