#### **9.2.2.4 Vital signs**

Vital signs include temperature, BP, and heart rate. They will be collected at every site visit prior to IMP administration. Weight will be collected at the screening Visit 1 (Day -28 to Day -1), Visit 2 (Week 0), Visit 6 (Week 12), Visit 9 (Week 24), Visit 11 (Week 40), and Visit 12 (Week 52). Weight should be taken with the patient wearing undergarments or very light clothing and no shoes and with an empty bladder. The same scale is recommended to be used throughout the study. Height will be collected at Visit 1 during screening only.

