#### **10.2.2.3 Visit 4-11 (Day 29±3 Week 4 to Day 281±3, Week 40)**

- Call IRT to register visit.

- Administer PRO questionnaires (EQ-5D-3L, FACIT-Fatigue, SF-36v2, HAQ-DI; Applicable only at **Visits 6 and 9**; at these visits PRO questionnaires should be completed prior to any significant interaction with the study team and prior to any physical examination or sampling).
- Review of concomitant medication.
- Dispense new patient diary and review last visit patient diary.
- Measure vital signs (including systolic and diastolic BP [mmHg], heart rate [beats per minute] and body temperature [°C]).
  - Measure body weight (kg) (Applicable only at Visits 6, 9 and 11)
  - Perform PMR clinical assessment for disease activity and flare.
  - Complete physician global assessment (MD-VAS) at Visits 6 and 9 only.
- Inquire about AEs/SAEs.
- Perform tuberculosis assessment.
  - Perform targeted physical examination (including head, eyes, ears, neck and throat, skin, respiratory, cardiovascular, neurologic, lymphatic examinations and abdominal examination) (**Applicable only at Visits 6, 9, and 11**).
  - Complete Glucocorticoid Toxicity Index questionnaire. (**Applicable only at Visits 6, 9 and 11**).
- Perform blood sampling at all visits (prior to administration of IMP) for the following tests:
  - CRP and ESR.
- Perform blood sampling (fasting, prior to administration of IMP) for the following tests: (**Applicable only at Visits 4, 6, 9 and 11**).
  - Hematology and chemistry.
  - Fasting lipids, fasting glucose and insulin.
  - HbA1c.
- Perform blood sampling (prior to administration of IMP) for the following tests: (**Applicable only at Visits 4, 6, 7, and 9**).
  - Serum sarilumab.  
**Note:** Additional sample is to be drawn 4-7 days after Visit 9 dosing. May be performed at the patient's home, if compatible with local organization.
- Perform blood sampling (prior to administration of IMP) for the following tests:
  - Anti-sarilumab antibody (Applicable only at Visits 6 and 9).
  - Biomarkers IL-6, sIL-6R. (Applicable only at Visits 6 and 9).
  - Immune Cell Phenotyping – Whole Blood (Applicable only at Visits 4 and 9).

- Future Use Samples – Plasma and Serum (Optional - requires separate signed consent form) (Applicable only at Visits 6 and 9).
- Perform urine pregnancy test (for WOCBP).
- Dispense and administer IMP.

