2.1.4.3 Laboratory safety variables

Clinical laboratory data will include hematology, clinical chemistry, and urinalysis. Clinical laboratory values will be converted to standard international units; international units will be used in all listings and tables. In addition, the lipids parameters will also be summarized in US units.

Hematology and chemistry data will be collected at screening, baseline, Weeks 4, 12, 24, 40, and 52, and/or early termination unless otherwise specified. The laboratory parameters will be classified as follows:

- Hematology
 - **Red blood cells and platelets and coagulation:** hemoglobin, hematocrit, platelet count, red blood cell (RBC) count, and RBC morphology (if RBC count is abnormal).
 - **White blood cells:** white blood cell (WBC) count and WBC differential (neutrophils, lymphocytes, monocytes, basophils, eosinophils).
- Clinical chemistry
 - **Metabolism:** fasting lipids (total cholesterol, high density lipoprotein cholesterol (HDL-C), low density lipoprotein cholesterol (LDL-C), ratio of HDL-C versus LDL-C (HDL-C:LDL-C), triglycerides), total proteins, CRP, fasting glucose, and hemoglobin A1c (HbA1c).
 - **Electrolytes:** sodium, potassium, chloride, calcium, phosphate, and bicarbonate.

- **Renal function:** creatinine, creatinine clearance, uric acid, and blood urea nitrogen (BUN).
- **Liver function:** alanine aminotransferase (ALT)/SGPT, aspartate aminotransferase (AST)/SGOT, alkaline phosphatase (ALP), albumin, total bilirubin, conjugated and unconjugated bilirubin, and lactate dehydrogenase (LDH).
- **Pregnancy test:** Serum β -hCG for all women of childbearing potential (screening only).
- **TB screen:** QuantiFERON®-TB Gold evaluation.
- **Hepatitis screen:** Hepatitis B and C serology, human immunodeficiency virus serology.

Urine samples will be collected as follows:

- **Urinalysis – dipstick:** pH, specific gravity, blood, glucose, protein, nitrates, leukocyte esterase, and bilirubin. If any parameter on the dipstick is abnormal, a urine sample was to be sent to the central laboratory for testing.

A urine pregnancy test was done for all women of childbearing potential at baseline, all visits up to Week 52 or early termination.

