2.4.5.3 Analyses of laboratory variables

The summary statistics (including number, mean, median, SD, minimum and maximum) of all laboratory variables (central laboratory values and changes from baseline) will be calculated for each visit or study assessment (baseline, each post baseline time point, endpoint) by treatment group. This section will be organized by biological function as specified in [Section 2.1.4.3](#).

In addition, for all laboratory parameters, the mean value and mean change from baseline at each scheduled visit during the treatment period will be plotted by treatment group.

The incidence of PCSAs (list provided in [Appendix C](#)) at any time during TEAE period will be summarized by biological function and treatment group whatever the baseline level and/or according to the following baseline status categories:

- Normal/missing
- Abnormal according to PCSA criterion or criteria

For lipids, the National Cholesterol Education Program Adult Treatment Panel III (NCEP ATP III) classification will be used for the baseline.

The incidence of abnormal laboratory values at any time during the TEAE period will be summarized in shift tables by biological function and treatment group whatever the baseline level and/or according to the following baseline status categories:

- Normal/Missing
- Abnormal high according to the normal range
- Abnormal low according to the normal range

Time to onset of the initial LDL-C elevation (≥ 4.1 mmol/L, ≥ 4.9 mmol/L), time to onset of the initial total cholesterol elevation (≥ 6.2 mmol/L), time to onset of the initial Grade 3 or Grade 4 neutropenia (neutrophil count < 1.0 Giga/L), time to onset of the initial platelet count < 100 Giga/L, time to onset of the initial lymphocyte count < 1.0 Giga/L, time to onset of the initial ALT elevation (> 3 x ULN, > 5 x ULN), time to onset of the initial AST elevation (> 3 x ULN, > 5 x ULN), and time to onset of initial total bilirubin > 2 x ULN will be analyzed using Kaplan-Meier estimates, using the midpoint of the time interval between the first assessment showing the elevation and the previous assessment, presented by treatment group.

Listings will be provided with flags indicating the out of range values as well as the PCSA values.

Neutrophils

The incidence of neutropenia by maximal grade (lowest absolute neutrophil count reported during the TEAE period) will be summarized. The 4 grades are defined as below:

- Grade 1: ≥ 1.5 Giga/L-LLN.

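### The SAP's safety 'endpoint' value normally falls back to Week 40 in completers and leaves the scheduled Week 52 value out of the endpoint row

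*SAP*

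**What the plan says.** The general rules in SAP 2.4.5 define the endpoint value for quantitative safety parameters from central laboratory or central reading measurements: "The endpoint value is commonly defined as the value collected at the same day/time of the last dose of investigational product". The fallback is: "If this value is missing, this endpoint value will be the closest one prior to the last dose intake". No period after the last dose is allowed, and the SAP does not say whether the last dose means the injection or the oral product.

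SAP 2.4.5.3 requires an endpoint row for laboratory variables, whose statistics "will be calculated for each visit or study assessment (baseline, each post baseline time point, endpoint) by treatment group". SAP 2.4.5.4 lists the same rows for vital signs.

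On dosing, note b to the protocol flow chart states: "Last administration of sarilumab is at Week 50". The Clinical Trial Summary gives both products: "last SC IMP administration at Week 50 and last oral IMP administration day before Visit 12".

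On sampling, SAP 2.1.4.3 says: "Hematology and chemistry data will be collected at screening, baseline, Weeks 4, 12, 24, 40, and 52, and/or early termination unless otherwise specified". For vital signs, Protocol 9.2.2.4 says: "They will be collected at every site visit prior to IMP administration". The flow chart has no visit between Week 40 and Week 52.

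**The concern.** An endpoint row should give one value per patient showing where that patient stood at the end of treatment. This matters most for neutrophils, platelets, transaminases and lipids, which the protocol introduction names among the risks of sarilumab. Under the rule as written, the row for a completer usually repeats Week 40 and ignores the sample taken at the end-of-treatment visit. For a patient who stops early, it can ignore the sample taken because treatment was stopped.

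The Week 52 sample is not an off-drug sample in any sense that the SAP uses elsewhere. The Week 4, 12, 24 and 40 laboratory samples are drawn before that day's injection, so each is nominally 14 days after the previous one. Week 52 is also nominally 14 days after an injection. The rule excludes it only because no further injection follows.

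**Working it through.** **Inputs.** Visit days and the ±3-day visit windows come from the flow chart (Protocol 1.2, SAP Appendix A). The ±3-day injection window comes from Protocol 8.1.1. Dosing ends as quoted above. Laboratory weeks are in SAP 2.1.4.3.

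**Day rule.** Day = 7 × week + 1. This reproduces every on-study visit day from Week 2 to Week 58, including Week 40 = 7 × 40 + 1 = 281 and Week 52 = 7 × 52 + 1 = 365. The same rule gives Week 50 = 351.

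**Latest scheduled value on or before the last dose, for a completer on the nominal schedule**

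| Reading of last dose | Day of last dose | Latest scheduled laboratory or vital-sign value |
|---|---|---|
| Injection (Week 50) | 351 | Day 281 (Week 40) |
| Oral (day before Visit 12) | 364 | Day 281 (Week 40) |

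**Gaps around the last injection**
- Week 40 to last injection: 351 − 281 = 70 days. With windows, 348 − 284 = 64 to 354 − 278 = 76.
- Last injection to Week 52: 365 − 351 = 14 days. With windows, 362 − 354 = 8 to 368 − 348 = 20.
- Injections every 2 weeks from Week 0 to Week 50 number 26. The Week 40 sample precedes that day's injection, so six (Weeks 40, 42, 44, 46, 48, 50) come after it: 6/26 = 23%.

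**How the SAP treats this time elsewhere.** The treatment epoch runs to the last injection + 13 days: 351 + 13 = Day 364, one day short of the nominal Week 52 visit. The treatment-emergent period runs to + 60 days: 351 + 60 = Day 411, which includes Week 52 (SAP 2.1.4).

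**Early stoppers.** Suppose the last injection is at home at Week 22 and the premature EOT visit is at Week 24, with no unscheduled values. On the injection reading, the endpoint value for hematology and chemistry is Week 12. The EOT value is excluded.

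**The case against.** A reader might infer that Week 52 data are never used, or that every completer is affected. The documents support neither.

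- **Week 52 is reported elsewhere.** The laboratory and vital-sign tables list each post-baseline time point next to the endpoint. Laboratory means are plotted by visit. Counts of potentially clinically significant abnormalities, laboratory shift tables and the neutropenia and thrombocytopenia grades use the treatment-emergent period. Only the endpoint row loses the value.
- **Unscheduled values count.** SAP 2.5.5 uses them for the last on-treatment value. One taken between Week 40 and the last dose would replace Week 40. Repeat tests are called for when ALT, neutrophils or platelets cross the protocol's thresholds (Protocol 10.8.2 to 10.8.4), so patients with those events are the likeliest to have a later value.
- **An early Visit 12 can qualify on the oral reading.** Protocol 8.1.2 has patients who come before the target date finish that week's blister pack. The Week 51 pack covers Days 358 to 364, so a visit on Days 362 to 364 may fall on or before the last oral dose.
- **A premature EOT visit can fall on the last-dose day.** Protocol 10.4.4 asks for it when treatment stops, where possible.
- **The wording is loose.** The rule says what is commonly done and names central measurements. It reaches vital signs only through the endpoint row in SAP 2.4.5.4.
- **An unlimited replacement would be worse.** A delayed EOT visit has no upper time limit, and a hold of 31 or more consecutive days counts as permanent (Protocol 10.4.1). A recovered, off-drug value could then be reported as the endpoint.

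All of these stand, and they narrow the point. None supplies another definition: SAP 2.5.5 mentions a last on-treatment value without defining it or linking it to SAP 2.4.5.

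**Conclusion.** The definition is wrong as written, with minor impact. For a completer dosed on schedule and without an unscheduled value after Week 40, the endpoint row shows a value about 70 days (64 to 76) before the last injection. It omits one taken 14 days (8 to 20) after that injection. Premature EOT values taken after the last dose are omitted too.

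This assumes that the rule is applied literally, that the last dose is the injection (or the oral dose on the nominal schedule), and that the vital-sign endpoint row uses the same definition. How many patients have no unscheduled value after Week 40 cannot be known from the documents, so no percentage of completers is claimed.

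A reader might also infer that a safety conclusion or a test is at risk. That does not follow: SAP 2.4.5 describes the safety analyses as essentially descriptive, and the abnormality counts already include Week 52.

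**What to change.** In SAP 2.4.5 replace the definition with: *The endpoint value is the last non-missing value (scheduled or unscheduled) after the first dose of SC IMP, up to and including the EOT visit and no later than a stated number of days after the last SC IMP dose.* State that it applies to both the laboratory and the vital-sign summaries.

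The limit must cover Week 52 with its windows, 8 to 20 days after the last injection; 21 days would do. The 13-day treatment epoch is too short, since it misses the nominal visit by one day. The 60-day treatment-emergent limit would admit more off-drug values.

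The cost is one sentence and a programming change, using data already collected. There is a small downside: in some early stoppers a value taken shortly after the last dose will enter the row, and the limit contains this. For completers seen at Visit 12 the row will usually match the Week 52 row, which suits a summary that also includes patients who stopped early.

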2.4.5.1 Analyses of adverse events

Generalities

The primary focus of AE reporting will be on TEAEs. Pre-treatment and post-treatment AEs will be described separately.

If an AE date/time of onset (occurrence, worsening, or becoming serious) is incomplete, an imputation algorithm will be used to classify the AE as pre-treatment, or TEAE, or post-treatment AE. The algorithm for imputing date/time of onset will be conservative and will classify an AE as treatment-emergent unless there is definitive information to determine it is pre-treatment or post-treatment. Details on classification of AEs with missing or partial onset dates are provided in [Section 2.5.3](#).

Adverse event incidence tables will present by SOC, HLGT, HLT, and PT, sorted in SOC internationally agreed order and then alphabetical order, and present the number (n) and percentage (%) of patients experiencing an AE by treatment group. Multiple occurrences of the same event in the same patient will be counted only once in the tables within a treatment phase. The denominator for computation of percentages is the safety population within each treatment group.

The tables by primary SOC and PT will be sorted by internationally agreed order of SOC and decreasing frequency of PT within SOC. Sorting will be based on results for the sarilumab 200mg arm.

Analysis of all treatment-emergent adverse events

The following TEAE summaries will be generated for the safety population.

- Overview of TEAEs, summarizing number (%) of patients with any
 - TEAE
 - Serious TEAE
 - TEAE leading to death
 - TEAE leading to permanent treatment discontinuation
- All TEAEs by primary SOC, HLGT, HLT, and PT, showing number (%) of patients with at least one TEAE sorted by SOC internationally agreed order. The other level (HLGT, HLT, PT) will be presented in an alphabetic order.
- All TEAEs by primary SOC and PT, showing number (%) of patients with at least one TEAE, sorted by SOC internationally agreed order and decreasing incidence of PTs within SOC. This sorting order will be applied to all other tables, unless otherwise specified.
- If > 10% patients are impacted by the COVID-19 pandemic: All TEAEs by primary SOC and PT by COVID-19 impact subgroup, showing number (%) of patients with at least one TEAE by COVID-19 impact subgroup.
- All COVID-19 TEAEs by primary SOC and PT, showing number (%) of patients with at least one COVID-19 related TEAE.
- All TEAEs by primary SOC, showing number (%) of patients with at least one TEAE, sorted by internationally agreed order of primary SOC.

- All TEAEs by relationship, presented by primary SOC, HLG, HLT, and PT, showing number (%) of patients with at least one TEAE, sorted by SOC internationally agreed order. The other level (HLG, HLT, PT) will be presented in an alphabetic order.
- All TEAEs by maximal severity, presented by primary SOC and PT, showing number (%) of patients with at least one TEAE by severity (ie, mild, moderate, or severe), sorted by sorting order defined above.

Analysis of all treatment emergent serious adverse event(s)

- All treatment-emergent SAEs by primary SOC, HLG, HLT, and PT, showing number (%) of patients with at least one serious TEAE, sorted by SOC internationally agreed order. The other level (HLG, HLT, PT) will be presented in an alphabetic order.
- All treatment-emergent SAEs by primary SOC and PT, showing number (%) of patients with at least one TEAE
- All treatment-emergent SAEs by primary SOC, showing number (%) of patients with at least one TEAE, sorted by internationally agreed order of primary SOC

Analysis of all treatment-emergent adverse event(s) leading to treatment discontinuation

- All TEAEs leading to treatment discontinuation, by primary SOC, HLG, HLT, and PT, showing number (%) of patients sorted by SOC internationally agreed order. The other level (HLG, HLT, PT) will be presented in an alphabetic order.
- All TEAEs leading to treatment discontinuation, by primary SOC and PT, showing number (%) of patients with at least one TEAE
- All TEAEs leading to treatment discontinuation, by primary SOC, showing number (%) of patients with at least one TEAE, sorted by internationally agreed order of primary SOC

Analysis of all treatment-emergent adverse event(s) leading to dose reduction

- For the management of pre-defined laboratory abnormalities, sarilumab dose can be reduced to 150 mg q2w. All treatment-emergent adverse events leading to dose reduction, by primary SOC, HLG, HLT and PT, showing the number (%) of patients, sorted by the sorting order defined above

Analysis AESI

Summaries of AESI defined by the search criteria:

- All treatment-emergent AESIs, by AESI category and PT, showing number (%) of patients, sorted by decreasing incidence of PT within each AESI category.
- Within each treatment-emergent AESI category, at a minimum the data display will include:
 - Overview summary
 - Treatment duration summary
 - Incidence by patient and by event

- Serious TEAEs
- TEAEs leading to treatment discontinuation
- TEAEs leading to death
- Possibly related TEAEs

